concern, expression of positive emotions, and self-confidence (Griffiths et al. 2006). The COM-R will also be assessed at the following time points: T7, and T12. Due to observers' availability, it is expected that the administration of the COM-R may not occur on the exact scheduled time point. However, every effort will be made to conduct this assessment as close to the required time points as possible.

Measures assessed 1 day before the sessions (T₁):

The STAI, HAD, POMS-SR, BDI, and BSI will be administered to assess for anxiety and depressive symptoms. As mentioned above, regarding pain assessment, the BPI-SF, MSAS, and MSKCC will be administered one day prior to the sessions as well.

Measures assessed just before drug administration (T₂):

The only measure to be administered will be the MSKCC to assess for pain.

Measures assessed throughout the sessions:

Ten minutes before and 30,60,90,120,180,240,300, and 360 minutes after capsule administration, monitor ratings, blood pressure, and heart rate will be obtained.

Blood pressure and heart rate:

Blood pressure (systolic, diastolic, and mean arterial pressure) and heart rate will be monitored.

Monitor rating questionnaire:

At the same points in time in which the above physiological measures will be obtained, the two session monitors will complete the Monitor Rating Questionnaire, which involves rating 20 dimensions of the subject's mood or behavior on a five-point Likert scale from 0 to 4.

Measure assessed 4 hours after drug administration (T₃):

The only measure to be administered will be the MSKCC to assess for pain.

Measures assessed 7 hours after drug administration (T₄):

The STAI, HAD, POMS-SR, BDI, and BSI will be administered to assess for anxiety and depression, and the BPI-SF, MSAS, and MSKCC will be administered to assess for pain.

Changes in state of consciousness will be assessed with the altered states of consciousness rating scale **5D-ASC** (Dittrich 1998; Dittrich, Lamparter et al. 1999), which is a scale suited to depict alterations in waking consciousness — including changes in mood, perception, experience of self and environment, and thought disorders — regardless of the inducing factor(s) (Dittrich 1996; Dittrich 1998). In addition, the Hallucinogen Rating Scale (**HRS**) will be administered, a 100-item scale used to assess altered states of consciousness produced by serotonergic hallucinogens such as psilocybin (Strassman 1994; Riba 2001).

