A data manager will be recruited and appointed prior to the initiation of the study. The funding for this study from the Heffter Research Institute includes monies to pay for a data manager.

Monitoring for Risk Minimization:

A physical examination will be performed which will include an EKG, urinalysis, and blood chemistry panels (liver and renal function tests and CBCs). An admission urine drug screen will be done for patient safety and protocol compliance. During each experimental treatment session, vital signs, including blood pressure and heart rate, will be taken 10 minutes before and 30,60,90,120,180,240,300, and 360 minutes after drug administration. Body temperature will be measured up to 30 minutes before and at six hours after drug administration. For these measurements, a window of ± 10 mins from the allocated time will facilitate the study flow.

Cardiovascular monitoring during a session:

1. Vital Signs are checked ten minutes before and 30,60,90,120,180,240,300, and 360 minutes after capsule administration and monitor ratings (blood pressure and heart rate) will be serially assessed.
2. Monitor Ratings: Blood pressure (systolic, diastolic, and mean arterial pressure) and heart rate will be monitored with an automated blood pressure machine.
3. If Systolic BP is > 160 or Diastolic is > 100 or Heart Rate is > 110 , vital signs will be checked every 5 minutes until systolic pressure is < 160 , diastolic pressure < 100 , and heart rate < 110
4. If Systolic BP is > 200 or Diastolic BP is > 110 for three readings (i.e. 15 minutes), the subject will receive sublingual Nitroglycerin 0.4 mg. If blood pressure readings do not decrease below these thresholds after 5 minutes of receiving the first dose of Nitroglycerin, the same dose of Nitroglycerin will be administered. A third dose of nitroglycerin will be given after another 5 minutes, if readings remain elevated above these levels (maximum dose is 0.4mg x 3 doses).
5. If blood pressure remains > 200 systolic or > 110 diastolic, at the judgment of the treating physician ([name]), the subject will be immediately transported to the nearby Bellevue Hospital Center Adult Emergency Room (AES) for further evaluation and treatment.

Aversive reactions to sublingual nitroglycerin:

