4) New Information indicating a change to the risks of potential benefits of the research, in terms of severity or frequency (i.e. Analysis indicates lower than expected response rate or a more severe or frequent side effect; Other research finds arms of study has no therapeutic value; FDA labeling change or withdrawal from marketing)

5) **Protocol Deviation or Violation. Only if:**

- a. Intended to eliminate apparent immediate hazard to a research participant, or
- b. Harmful (caused harm to participants or others, or placed them at increased risk of harm, or
- c. Possible serious or continued noncompliance

6) **Complaint**

- a. Unresolved by the research team, or
- b. That indicates increased or unexpected risks

7) **Incarceration** when in the opinion of the PI it is in the best interest of the participant to remain on the study

F. Frequency of Review and Rationale for Recommended Frequency

1) At a minimum the DSMB will meet quarterly or after a cohort of 5 patients has completed the study, whichever is more frequent.

2) The DSMB will meet more regularly as necessary to review any AEs, serious AEs, UAPs, or new information that in the opinion of the PI or DSMB may impact risks or study continuation.

Pharmacology and toxicology information:

Please refer to IND No. 56,530, submitted by [name], M.D. of the University of Arizona.

Previous human experience with the investigational drug (Safety Profile):

Psilocybin is 4-hydroxy-N,N-dimethyltryptamine, and occurs in nature in many species of mushrooms, including the genera Psilocybe, Conocybe, Gymnopilus, Panaeolus and Stropharia. As is the case with LSD and mescaline, psilocybin is an extremely potent agonist at 5-HT(2A) and 5-HT(2C) receptors, and their

binding potency to these receptors is directly correlated with their human potency as hallucinogens. (Delgado & Moreno, 1998) Although not provided the extensive degree of investigation received by the prototype hallucinogen, LSD, psilocybin was subjected to a variety of research studies during the 1960s employed to establish its psychopharmacological profile of action. Psilocybin was determined to be active and generally safe in the 100 to 300 µg/Kg range (Moreno, 1998). The experience lasts from 4 to 6 hours.

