Regarding the issue of potential adverse psychological effects, these include the relative risks associated with alterations of perception, flashbacks and the low probability of dizziness, nausea, vomiting, headaches, increased pulse, transient moderate to severe elevation in blood pressure, dilated pupils and slightly elevated temperature. Actual reports of psilocybin induced psychosis are very rare. Although psychosis has been associated with the use of hallucinogens, the vast majority of cases are from uncontrolled, recreational use. Sidney Cohen, a distinguished psychiatric researcher at the UCLA School of medicine from the 1950s to 1980s, examined the use of hallucinogens in research settings and estimated the incidence of hallucinogen related psychosis to be about 0.8/1000 experimental subjects (Cohen, 1960). Harvard Medical School psychiatrist Lester Grinspoon has described the risks of hallucinogens within treatment settings: “The main danger in psychedelic drug therapy is the same as the danger of any deep-probing psychotherapy: if the unconscious material that comes can be neither accepted and integrated nor totally repressed, symptoms may become worse, and even psychosis or suicide is possible. But the potential for harm has been exaggerated, for two reasons. First, much irrational fear and hostility is left over from the cultural wars of the sixties. More generally, we tend to misconceive drugs as something utterly different from and almost by definition more dangerous than other ways of changing mental processes; actually the dangers in work with LSD do not seem obviously greater than in comparable forms of therapy aimed at emotional insight” (Grinspoon and Bakalar, 1979). From the 1950s to 1970s an extensive literature emerged from experimentation into the controlled use of hallucinogens in the treatment of psychiatric patients. Lester Grinspoon has described that “between 1950 and the mid-1960s there were more than a thousand clinical papers discussing 40,000 patients, several dozen books and six international conferences on psychedelic drug therapy. . .many people remember vaguely that LSD and other psychedelic drugs were once used. This was not a quickly rejected and forgotten fad” (Grinspoon and Bakakar, 1979). The model identified as being most efficacious, involving careful attention to developing optimal set (preparation, intention and underlying psychological predisposition) and setting (environmental and interpersonal context), often involved the administration of the active agent on only one occasion. It is important to point out, however, that the one-time hallucinogen facilitated experience occurred within the context of an ongoing psychotherapeutic process. The long-term effects of this single dose experience when utilized in optimal context were often therapeutic.

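### With one post-dose temperature reading, at six hours, the scheduled data cannot show peak temperature or a rise that resolves before about 350 minutes

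*Combined protocol and SAP*

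**What the plan says.** Under Monitoring for Risk Minimization, temperature has its own sentence: "Body temperature will be measured up to 30 minutes before and at six hours after drug administration". The next sentence adds: "For these measurements, a window of ± 10 mins from the allocated time will facilitate the study flow". The same section says that in each session "vital signs, including blood pressure and heart rate, will be taken 10 minutes before and 30,60,90,120,180,240,300, and 360 minutes after drug administration".

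Measures assessed throughout the sessions gives the same time grid and names what is recorded on it: "minutes after capsule administration, monitor ratings, blood pressure, and heart rate will be obtained". Temperature is not on that list.

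The safety profile (Previous human experience with the investigational drug) says of psilocybin that "The experience lasts from 4 to 6 hours". Its list of potential adverse effects ends with "transient moderate to severe elevation in blood pressure, dilated pupils and slightly elevated temperature". That part of the list is introduced as being of low probability.

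Safety is part of the secondary feasibility objective, and Planned DSMB Review includes vital signs in the safety information to be assessed. The documents give no time course for temperature, no temperature threshold and no rule on unscheduled temperature readings.

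**The concern.** The protocol names temperature as something the drug may change, then measures it after dosing only when the stated duration of the experience is ending or has ended. Pulse and blood pressure appear in the same list of effects and are sampled eight times. No reason is given for the single temperature reading.

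What is at stake is how the temperature data will be read. A rise that has gone by six hours is recorded as no change. A table of pre-dose and six-hour values that shows nothing could then be taken, by the DSMB or in a report, to mean that temperature was unaffected, when the hours in between were not sampled. Symptoms are a weak substitute for separating the agents, because the section on niacin lists flushing with warmth among that agent's own side effects. The cancer study described in the Rationale and Background used 0.2 mg/kg against 0.3 mg/kg here, so it does not directly supply the missing information at this dose.

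**Working it through.** The plan has no figure to reproduce here. The check sets the measurement schedule against the stated duration.

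**Inputs from the documents**
- Temperature: one reading between 30 and 0 minutes before dosing, and one at 6 h = 360 min.
- Window: ±10 min.
- Blood pressure and heart rate, post-dose: 30, 60, 90, 120, 180, 240, 300 and 360 min.
- Stated experience: 4 to 6 h = 240 to 360 min.

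**1. When the post-dose temperature is taken.** 360 − 10 = 350 min and 360 + 10 = 370 min, that is 5.83 to 6.17 h.

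**2. Time with no scheduled temperature.** Shortest: 350 − 0 = 350 min. Longest: 370 + 30 = 400 min.

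**3. Number of readings.** Temperature has 1 post-dose reading. Blood pressure and heart rate have 8, of which 7 fall before 350 min.

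**4. Position relative to the end of the experience** (reading time minus end of experience)

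| Experience lasts | Nominal reading | Range with window |
|---|---|---|
| 4 h (240 min) | 360 − 240 = 120 min after | 110 to 130 min after |
| 5 h (300 min) | 360 − 300 = 60 min after | 50 to 70 min after |
| 6 h (360 min) | 360 − 360 = 0 min | 10 min before to 10 min after |

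**5. Which rises the schedule would record.** The intervals below are assumptions, since the documents give none. A rise from a to b minutes is recorded at the nominal time only if a ≤ 360 ≤ b.

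| Assumed rise (min) | Recorded at 360 min? | Blood pressure and heart rate times inside it |
|---|---|---|
| 60–180 | No | 4 |
| 90–240 | No | 4 |
| 120–300 | No | 4 |
| 120–360 | Yes | 5 |
| 120–400 | Yes | 5 |

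Allowing for the window, a rise that is over before 350 min is missed whenever the reading is taken. One that has begun by 350 min and lasts to 370 min or beyond is recorded whenever the reading is taken. One that ends between 350 and 370 min may or may not be recorded.

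**6. Effect of added readings.** A reading at 120 min falls inside all three of the missed intervals. A reading at 240 min falls inside 90–240 and 120–300. Even a few of the existing times between 60 and 240 min would therefore change the result under these assumptions.

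**The case against.** The strongest reply is that unequal sampling matches unequal hazards. The safety profile describes the blood pressure effect as moderate to severe but the temperature effect as slight, and calls the group improbable. It also reports physiologically safe administration at 0.045 to 0.43 mg/kg in volunteers and 0.025 to 0.3 mg/kg in patients with OCD. The treatment team stays with the subject, nothing bars an unscheduled reading, and a symptomatic rise could be noticed and recorded as an adverse event. The statistical section plans no comparison of temperature by agent. The schedule is clear, can be carried out, and contradicts no other passage.

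Most of this stands, and it limits the weight of the point. It does not make the six-hour value informative about the hours before it.

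A reader might go further and infer that a rise during the session cannot be detected, or that the two agents are bound to look alike on temperature. The documents do not support either. A rise still present at about 350 to 370 minutes would be recorded and could differ between agents. Nor can one say that no reading falls in the period when a rise would occur: the 4 to 6 hours describe the experience, and nothing says when temperature rises or returns to normal.

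In the other direction, one might argue that the word *including* in the vital-signs sentence already puts temperature on the eight-point grid. The separate temperature sentence and the list under Measures assessed throughout the sessions both weigh against that reading.

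**Conclusion.** The point holds as a modest gap in the safety data, of low severity. One scheduled post-dose reading at 350 to 370 minutes cannot give peak temperature or the frequency of transient elevation, and a normal value at that time should not be read as showing that no rise occurred.

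That the schedule is uninformative about the earlier hours follows from the schedule alone. Whether any rise is in fact missed depends on an assumption the documents do not settle, namely that a rise, if there is one, resolves before about 350 minutes. The size of the gap is 350 to 400 minutes without a scheduled temperature. The number of events missed cannot be estimated from the documents. No endpoint, power figure or planned efficacy analysis is affected.

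**What to change.** In Monitoring for Risk Minimization, add body temperature at some of the vital-sign times already scheduled between 60 and 240 minutes (60, 90, 120, 180, 240), and keep the pre-dose and six-hour readings. Use the same times in both sessions, and list temperature under Measures assessed throughout the sessions for those times. In the statistical section, add a descriptive summary by agent of the maximum post-dose change from the pre-dose reading. If the sponsor prefers the single reading, the protocol should say why it is enough given the named effect and the stated duration.

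The cost is a one-line amendment and a short reading when staff are already taking blood pressure and heart rate. The downside is a brief extra interruption for a subject who is lying down with eye shades and music. The maximum would still be the highest of the scheduled readings, not a true peak.

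If the sessions are already complete, the remedy is in reporting: state that temperature was scheduled only before dosing and at six hours, and that these data do not exclude a rise in between. This concerns measurement only; no treatment rule is proposed.

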b. Events and Information requiring reporting to the NYU IRB and FDA in clinical trials of drug and biological products conducted under IND regulations (under Title 21 of the Code of Federal Regulations {21 CFR} part 56 {Institutional Review Boards}, part 312 {Investigational New Drug Application}:

Unanticipated Problems involving risks to participants or others (UAPS)

UAPS are events (including internal or external events, deaths¹, life-threatening experiences¹, injuries, breaches of confidentiality or other problems) that occur any time during or after the research study, which in the opinion of the DSMB or the PI are:

a) **Unanticipated (unexpected)**- not in the consent form, investigator brochure, protocol, package insert, or label; or unanticipated in its frequency, severity or specificity,

AND

b) **Harmful** –caused harm to participants or others, or placed them at increased risk of harm

AND

c) **Serious**- resulting in death or injury requiring hospitalization (admission)

AND

d) **Related** to the research procedures- caused by, or probably caused by research activity

¹Unanticipated deaths or life-threatening experiences related to the research will be reported to the NYU IRB, BCCR and the FDA in a written INDS safety report of ‘any adverse experience associated with the use of the drug that is both serious and unexpected (§ 312.32(c)(1)(i)(A),(B)) within **24** hours. Otherwise, all other UAPS will be reported to the NYU IRB and FDA within **5** days.

Other reportable events and information

1) A single occurrence, or small number of occurrences of a serious, unexpected event that is not commonly associated with drug exposure, but uncommon in the study population

2) Multiple occurrences of an AE that, based on an aggregate analysis, is determined to be an unanticipated problem. There should be a determination that the series of AEs represents a signal that the AEs were not just isolated occurrences and involve risk to human subjects

3) An AE that is described or addressed in the investigator’s brochure, protocol, or informed consent documents, but occurs at a specificity or severity that is inconsistent with prior observations.

4) New Information indicating a change to the risks of potential benefits of the research, in terms of severity or frequency (i.e. Analysis indicates lower than expected response rate or a more severe or frequent side effect; Other research finds arms of study has no therapeutic value; FDA labeling change or withdrawal from marketing)

5) **Protocol Deviation or Violation. Only if:**

- a. Intended to eliminate apparent immediate hazard to a research participant, or
- b. Harmful (caused harm to participants or others, or placed them at increased risk of harm, or
- c. Possible serious or continued noncompliance

6) **Complaint**

- a. Unresolved by the research team, or
- b. That indicates increased or unexpected risks

7) **Incarceration** when in the opinion of the PI it is in the best interest of the participant to remain on the study

F. Frequency of Review and Rationale for Recommended Frequency

1) At a minimum the DSMB will meet quarterly or after a cohort of 5 patients has completed the study, whichever is more frequent.

2) The DSMB will meet more regularly as necessary to review any AEs, serious AEs, UAPs, or new information that in the opinion of the PI or DSMB may impact risks or study continuation.

Pharmacology and toxicology information:

Please refer to IND No. 56,530, submitted by [name], M.D. of the University of Arizona.

Previous human experience with the investigational drug (Safety Profile):

Psilocybin is 4-hydroxy-N,N-dimethyltryptamine, and occurs in nature in many species of mushrooms, including the genera Psilocybe, Conocybe, Gymnopilus, Panaeolus and Stropharia. As is the case with LSD and mescaline, psilocybin is an extremely potent agonist at 5-HT(2A) and 5-HT(2C) receptors, and their

binding potency to these receptors is directly correlated with their human potency as hallucinogens. (Delgado & Moreno, 1998) Although not provided the extensive degree of investigation received by the prototype hallucinogen, LSD, psilocybin was subjected to a variety of research studies during the 1960s employed to establish its psychopharmacological profile of action. Psilocybin was determined to be active and generally safe in the 100 to 300 µg/Kg range (Moreno, 1998). The experience lasts from 4 to 6 hours.

Research with psilocybin has resumed within the last several years and has been safely given to normal volunteers, regarding physiological parameters, at doses ranging from 0.045mg/kg to 0.43mg/kg (Hasler et al. 2004; Griffiths et al. 2006). It has also been safely administered, again regarding physiological parameters, to patients with OCD at doses ranging from 0.025mg/kg to 0.3mg/kg (Moreno et al. 2006). Moreover, a completed double-blind, placebo-controlled (niacin as the control), Phase I study with a cross-over design at Harbor-UCLA Medical was conducted by [name], where patients with advanced cancer and anxiety received a single dose of 0.2mg/kg of psilocybin. In total, 12 out of 12 patients were enrolled and completed the study. As mentioned above, the study established the safety and feasibility of administering a moderate dose of psilocybin to patients with advanced cancer and anxiety. Some of the data suggested a treatment effect with reduction in anxiety and depressive symptoms (Grob 2010).

Regarding the issue of potential adverse psychological effects, these include the relative risks associated with alterations of perception, flashbacks and the low probability of dizziness, nausea, vomiting, headaches, increased pulse, transient moderate to severe elevation in blood pressure, dilated pupils and slightly elevated temperature. Actual reports of psilocybin induced psychosis are very rare. Although psychosis has been associated with the use of hallucinogens, the vast majority of cases are from uncontrolled, recreational use. Sidney Cohen, a distinguished psychiatric researcher at the UCLA School of medicine from the 1950s to 1980s, examined the use of hallucinogens in research settings and estimated the incidence of hallucinogen related psychosis to be about 0.8/1000 experimental subjects (Cohen, 1960). Harvard Medical School psychiatrist Lester Grinspoon has described the risks of hallucinogens within treatment settings: “The main danger in psychedelic drug therapy is the same as the danger of any deep-probing psychotherapy: if the unconscious material that comes can be neither accepted and integrated nor totally repressed, symptoms may become worse, and even psychosis or suicide is possible. But the potential for harm has been exaggerated, for two reasons. First, much irrational fear and hostility is left over from the cultural wars of the sixties. More generally, we tend to misconceive drugs as something utterly different from and almost by definition more dangerous than other ways of changing mental processes; actually the dangers in work with LSD do not seem obviously greater than in comparable forms of therapy aimed at emotional insight” (Grinspoon and Bakalar, 1979). From the 1950s to 1970s an extensive literature emerged from experimentation into the controlled use of hallucinogens in the treatment of psychiatric patients. Lester Grinspoon has described that “between 1950 and the mid-1960s there were more than a thousand clinical papers discussing 40,000 patients, several dozen books and six international conferences on psychedelic drug therapy. . .many people remember vaguely that LSD and other psychedelic drugs were once used. This was not a quickly rejected and forgotten fad” (Grinspoon and Bakakar, 1979). The model identified as being most efficacious, involving careful attention to developing optimal set (preparation, intention and underlying psychological predisposition) and setting (environmental and interpersonal context), often involved the administration of the active agent on only one occasion. It is important to point out, however, that the one-time hallucinogen facilitated experience occurred within the context of an ongoing psychotherapeutic process. The long-term effects of this single dose experience when utilized in optimal context were often therapeutic.
